9.1 Discontinuation and completion

9.1.1 Study treatment discontinuation and study discontinuation

Discontinuation of study treatment for a participant only applies to those in the inclisiran treatment group and occurs when study treatment is stopped earlier than the protocol planned duration. Discontinuation of inclisiran can be initiated by either the participant or the investigator.

The investigator must discontinue treatment with inclisiran for a given participant if, he/she believes that continuation would negatively impact the participant's well-being.

Study treatment of inclisiran must be discontinued under the following circumstances

- Participant/guardian decision
- Pregnancy
- Use of prohibited treatment as per recommendations in the prohibited treatment section
- Any situation in which study participation might result in a safety risk to the participant
- Any severe suspected drug related AE at the investigator's discretion

If discontinuation of study treatment occurs, the investigator should make a reasonable effort to understand the primary reason for the participant's premature discontinuation of study treatment and record this information.

Participants who discontinue study treatment or who decide they do not wish to participate in the study further should NOT be considered withdrawn from the study UNLESS they withdraw their consent (see 'Withdrawal of Informed Consent' section). Where possible, they should return for the assessments indicated in the Assessment Schedule. If they fail to return for these assessments for unknown reasons, every effort (e.g., telephone, e-mail, letter) should be made to contact the participant/pre-designated contact as specified in the lost to follow-up section. This contact should preferably be done according to the study visit schedule. Unless a participant withdraws informed consent, personal and coded data are able to be collected in accordance with the informed consent form.

If the participant cannot or is unwilling to attend any visit(s), the site staff should maintain regular telephone contact with the participant, or with a person pre-designated by the participant. This telephone contact should preferably be done according to the study visit schedule.

After study treatment discontinuation, at a minimum, in abbreviated visits, the following data should be collected at clinic visits or via telephone/email contact:

- New / concomitant treatments
- Adverse Events / Serious Adverse Events

The investigator must also contact the IRT to register the participant's discontinuation from study treatment.

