Clinical Trial Team	A group of people responsible for the planning, execution and reporting of all clinical trial activities. Examples of team members include the Study Lead, Medical Monitor, Trial Statistician etc.		
Coded Data	Personal Data which has been de-identified by the investigative center team by replacing personal identifiers with a code.		
Cohort	A specific group of participants fulfilling certain criteria and generally treated at the same time		
Control drug	A study drug (active or placebo) used as a comparator to reduce assessment bias, preserve blinding of investigational drug, assess internal study validity, and/or evaluate comparative effects of the investigational drug		
Discontinuation from study	Point/time when the participant permanently stops receiving the study treatment and further protocol required assessments or follow-up, for any reason. No specific request is made to stop the use of their samples or data.		
Discontinuation from study treatment	Point/time when the participant permanently stops receiving the study treatment for any reason (prior to the planned completion of study drug administration, if any). Participant agrees to the other protocol required assessments including follow-up. No specific request is made to stop the use of their samples or data.		
Dosage	Dose of the study treatment given to the participant in a time unit (e.g. 100 mg once a day, 75 mg twice a day)		
Electronic Data Capture (EDC)	Electronic data capture (EDC) is the electronic acquisition of clinical study data using data collection systems, such as Web-based applications, interactive voice response systems and clinical laboratory interfaces. EDC includes the use of Electronic Case Report Forms (eCRFs) which are used to capture data transcribed from paper source forms used at the point of care		
End of the clinical trial	The end of the clinical trial is defined as the last visit of the last participant or at a later point in time as defined by the protocol		
Enrollment	Point/time of participant entry into the study at which informed consent must be obtained		
eSource (DDE)	Electronic source (eSource) Direct Data Entry (DDE) refers to the capture of clinical study data electronically, at the point of care. eSource Platform/Applications combines source documents and case report forms (eCRFs) into one application, allowing for the real time collection of clinical trial information to sponsors and other oversight authorities, as appropriate		

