4.1.1 Rationale for choice of background therapy

Participants are required to be receiving statin therapy, or have documentation of statin intolerance, at the time of identification and screening (~2-5 wks following an ACS) without plans to adjust lipid lowering therapy at that point in time. Adjustments in lipid-lowering therapy other than inclisiran during the study will occur at the discretion of the treating (primary) health care practitioner in both treatment groups, mimicking real-world clinical decision-making. Inclisiran will not be excluded from the usual care group post-approval – it is assumed based on historical and anticipated product uptake shortly after launch that potential inclisiran treatment in the usual care group will be minimal and thus will not significantly interfere with the study. Participants receiving inclisiran during the trial should not be simultaneously treated with a PCSK9 inhibiting monoclonal antibody.

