6.2.2 Prohibited medication

The treatments displayed in the table below are not allowed to be used simultaneously with inclisiran in the treatment arm. No modifications of therapy is required or recommended in the usual care arm.

Medication	Prohibition period	Action to be taken
Alirocumab (Praluent)	Participants randomized to inclisiran: monoclonal antibodies directed against PCSK9 are prohibited for the full duration of the study	Discontinue PCSK9 inhibitor
Evolocumab (Repatha)	Participants randomized to inclisiran: monoclonal antibodies directed against PCSK9 are prohibited for the full duration of the study	Discontinue PCSK9 inhibitor

Table 6-2 Prohibited medication

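### Protocol 6.2.2/Table 6-2 and 9.1.1 conflict on which drug is stopped when a participant randomized to inclisiran receives a PCSK9 antibody

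*Protocol*

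**What the plan says.** **Prohibited medication (Protocol 6.2.2 and Table 6-2).** The lead sentence reads: "The treatments displayed in the table below are not allowed to be used simultaneously with inclisiran in the treatment arm". The table names two drugs, alirocumab and evolocumab. For participants randomized to inclisiran, each row says that "monoclonal antibodies directed against PCSK9 are prohibited for the full duration of the study". The action column for both rows reads "Discontinue PCSK9 inhibitor". Inclisiran is not mentioned as something to stop.

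**Stopping rule (Protocol 9.1.1).** The list is introduced by "Study treatment of inclisiran must be discontinued under the following circumstances", and one of its bullets is "Use of prohibited treatment as per recommendations in the prohibited treatment section". The protocol glossary defines discontinuation from study treatment as the "Point/time when the participant permanently stops receiving the study treatment for any reason", so the stop is permanent.

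**SAP.** Sections 1.2.1 and 2.5.3 list discontinuation of study treatment (event 2) and use of PCSK9 antibodies in the inclisiran arm (event 3) as separate intercurrent events. Both are ignored in the primary analysis. Section 2.5.6 drops data after any of the listed events in a supplementary MMRM. Section 2.2 restricts the inclisiran arm of Restricted Set 2 to participants who received all three doses.

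**Usual care arm.** Protocol 4.1.1 says: "Participants receiving inclisiran during the trial should not be simultaneously treated with a PCSK9 inhibiting monoclonal antibody"; section 3 carries a similar note. Section 6.2.2 says: "No modifications of therapy is required or recommended in the usual care arm".

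**The concern.** The two antibodies are the only prohibited treatments in the protocol, so they are exactly what triggers the 9.1.1 bullet. One section tells the site to stop the antibody. The other uses mandatory language to stop inclisiran, and supports it by pointing to a section that does not say so.

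The situation is foreseeable. Lipid-lowering therapy other than study inclisiran is managed by a treating physician who does not run the study visits and does not see the study LDL-C values (Protocol 3, 4.1 and 4.1.1). The sponsor anticipated antibody use in this arm when it added it as an intercurrent event (SAP section 4, item 7).

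At stake is a mandatory treatment instruction that sites can apply in different ways. The consequences fall on one arm only, and they reach LDL-C values that the primary analysis keeps.

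**Working it through.** No figure in the plan bears on this point, so the check is a comparison of texts followed by a count of doses.

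**1. The possible readings.**

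| Reading | Antibody | Inclisiran |
|---|---|---|
| Both sections applied literally | Stopped, and barred for the rest of the study because the bar follows the randomized arm | Permanently stopped |
| 9.1.1 taken as deferring to Table 6-2 | Stopped | Continues |

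Under the first reading the participant receives neither PCSK9-directed agent from then on. Statin and other permitted lipid-lowering therapy can continue (Protocol 3). A third course, stopping inclisiran and leaving the antibody in place, breaches the table rows, which bar the antibody for the full study. The lead sentence of 6.2.2 speaks only of simultaneous use, so the section is not entirely clear within itself, but the rows are explicit.

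**2. Does other text settle it?** Protocol 6.2.1 tells the site to contact the sponsor about a drug in doubt and about whether an enrolled participant should continue in the study. It does not say which drug stops. Protocol 6.5.1 allows a restart once the reason for stopping has resolved, but that sentence follows a list of adverse event, liver and CK reasons that does not include prohibited medication. No passage sets an order of precedence.

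**3. Study doses that depend on the reading.** Three doses are planned, at Days 0, 90 and 270 (Protocol 4.2). If inclisiran is stopped because of antibody use, the number of doses lost is three minus those already given:

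- after Day 0 and before the Day 90 dose: 3 − 1 = 2
- after the Day 90 dose and before the Day 270 dose: 3 − 2 = 1
- after the Day 270 dose: 3 − 3 = 0

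The reading therefore changes the doses given only if the event precedes the Day 270 dose.

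**4. What changes in the analysis.**

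- *Event classification.* Event 3 is identified from coded medication records (SAP Table 2-3), so any antibody use in the inclisiran arm is event 3 under either reading. Stopping inclisiran adds event 2.
- *Primary analysis.* Both events are ignored, so the method and the set of included values are the same. The Day 330 LDL-C value itself may differ if doses were omitted.
- *Supplementary MMRM.* Data are cut after the first event. Where antibody use is what prompts the stop, the cut falls at antibody use under both readings.
- *Restricted Set 2.* A participant who loses one or two doses drops out of the set; one who continues with all three doses stays in.
- *Disposition and exposure.* Treatment discontinuations (SAP 2.3.1) and duration of exposure (SAP 2.1.1) can differ with the reading.

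**The case against.** The strongest defence is that the 9.1.1 bullet does not stand alone. Its closing words tie it to the prohibited treatment section, so Table 6-2 governs and only the antibody stops. The bullet can still be given effect by taking it to apply where the antibody is not in fact stopped. Protocol 6.2.1 also provides a route to the sponsor, so sites are not left wholly to themselves.

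This reading is available but not compelled. The condition that would rescue the bullet is written nowhere, and a site that takes a mandatory stop rule at face value is not misreading it. The route to the sponsor helps only a site that recognises a doubt, and it does not supply the answer.

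Other parts of the defence do stand. A reader might infer that the site's action decides whether a case is event 2 or event 3. It does not: event 3 applies regardless, and event 2 may be added. A reader might also infer that the participant is left untreated. The documents do not support that: background therapy continues, and Protocol 1.1.5 describes the effect of doses already given as sustained.

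In the usual care arm, the apparent clash is a minor tension. Sections 3 and 4.1.1 give a general caution against the combination, and 6.2.2 says that the protocol calls for no change of therapy in that arm. Protocol 4.1.1 expects commercial inclisiran use there to be minimal.

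**Conclusion.** The conflict is in the current text and holds: for the same event, Table 6-2 stops the antibody and 9.1.1 stops inclisiran, with no rule on which prevails. It is an inconsistency in mandatory treatment instructions. It can make sites differ in remaining inclisiran doses (for events before the Day 270 dose), Day 330 LDL-C, counted treatment discontinuations and Restricted Set 2 membership. It does not alter the primary analysis method, the significance level or the sample size.

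No effect size is claimed, because the documents do not say how often antibodies are started in this arm. A reader might be tempted to assume that 5% of the arm is affected, that half of those stop inclisiran, and that each loses 50 percentage points, giving 0.05 × 0.5 × 50 = 1.25 points against the planned difference of 15. The documents do not support that figure. The 5% and the half have no source, and the 50 assumes complete loss of an effect that the protocol calls sustained. It also ignores that stopping after the Day 270 dose removes no study dose.

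No view is given here on which clinical rule should stand.

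**What to change.** Reconcile Protocol 6.2.2/Table 6-2 with 9.1.1 so that a single instruction, chosen by the sponsor, covers antibody use in a participant randomized to inclisiran. It should say what happens to each of the two drugs. Put the same wording in both places and issue it to sites.

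As a minor matter, align the caution in sections 3 and 4.1.1 on combining inclisiran with an antibody with the 6.2.2 statement on the usual care arm.

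If study visits are already complete, list the affected inclisiran-arm participants with the action taken and the doses received, so that any difference in site practice is visible.

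The cost is protocol wording in these sections and a site memo. The SAP's event definitions already cover the cases, and sample size, procedures and analysis methods are untouched.

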9.1.2 Withdrawal of informed consent

Participants may voluntarily withdraw consent to participate in the study for any reason at any time. Withdrawal of consent occurs only when a participant:

Does not want to participate in the study anymore,

and

Does not want any further visits or assessments

and

Does not want any further study related contacts

In this situation, the investigator should make a reasonable effort (e.g., telephone, e-mail, letter) to understand the primary reason for the participant's decision to withdraw his/her consent and record this information.

Study treatment for participants in the inclisiran + usual care treatment group must be discontinued with no more inclisiran injections planned. In both the inclisiran + usual care and the usual care group no further assessments are to be conducted, and the data that would have been collected at subsequent visits will be considered missing.

Further attempts to contact the participant are not allowed unless safety findings require communicating or follow-up.

All efforts should be made to complete the assessments prior to study discontinuation. A final evaluation at the time of the participant's study discontinuation should be made as detailed in the assessment table.

Novartis will continue to retain and use all research results (data) that have already been collected for the study evaluation.

9.1.3 Lost to follow-up

For participants whose status is unclear because they fail to appear for study visits without stating an intention to discontinue or withdraw, the investigator must show "due diligence" by documenting in the source documents steps taken to contact the participant, e.g., dates of telephone calls, registered letters, etc. A participant should not be considered as lost to followup until due diligence has been completed or until the end of the study.

9.1.4 Early study termination by the sponsor

The study can be terminated by Novartis at any time.

Reasons for early termination, include the following:

- Unexpected, significant, or unacceptable safety risk to participants enrolled in the study
- Decision based on recommendations from applicable board(s) after review of safety and efficacy data
- Discontinuation of study drug development

In taking the decision to terminate, Novartis will always consider participant welfare and safety. Should early termination be necessary, participants must be seen as soon as possible and treated as a prematurely withdrawn participant. The investigator may be informed of additional procedures to be followed in order to ensure that adequate consideration is given to the protection of the participant's interests. The investigator or sponsor depending on local regulation will be responsible for informing IRBs/IECs of the early termination of the trial.

9.2 Study completion and post-study treatment

At the study completion/end of study visit, including participants who are prematurely withdrawn from the study, the referring or primary physician will continue to provide ongoing medical care. When the participant has completed all scheduled study assessments, the investigator must call the IRT to record the participant completion in the IRT.

Study completion is defined as when the last participant finishes their Study Completion visit and any repeat assessments associated with this visit have been documented and followed-up appropriately by the investigator or, in the event of an early study termination decision, the date of that decision (e.g., each participant will be required to complete the study in its entirety and thereafter there will be no further study treatments provided (i.e., no further inclisiran injections will be conducted).

For study participants who have successfully completed the study, further guidance will be provided separately concerning continuation of treatment and access to investigational drug. This guidance will be provided to sites prior to the completion visit of the first patient

(first patient last visit). For study participants who terminate prior to the end of the study or who withdraw from treatment, continuing treatment should be managed by the investigator and/or referring or primary physician

Safety monitoring and reporting 10

10.1 Definition of adverse events and reporting requirements

10.1.1 Adverse events

An adverse event (AE) is any untoward medical occurrence (e.g., any unfavorable and unintended sign [including abnormal laboratory findings], symptom or disease) in a clinical investigation participant after providing written informed consent for participation in the study. Therefore, an AE may or may not be temporally or causally associated with the use of a medicinal (investigational) product.

The investigator has the responsibility for managing the safety of individual participant and identifying adverse events.

Novartis qualified medical personnel will be readily available to advise on trial related medical questions or problems.

The occurrence of adverse events must be sought by non-directive questioning of the participant at each visit during the study. Adverse events also may be detected when they are volunteered by the participant during or between visits or through physical examination findings, laboratory test findings, or other assessments.

Adverse events must be recorded under the signs, symptoms, or diagnosis associated with them, accompanied by the following information (as far as possible) (if the event is serious refer to Section 10.1.2):

- 1. The severity grade
 - mild: usually transient in nature and generally not interfering with normal activities
 - moderate: sufficiently discomforting to interfere with normal activities
 - severe: prevents normal activities
- 2. Its relationship to the study treatment. If the event is due to lack of efficacy or progression of underlying illness (i.e., progression of the study indication) the assessment of causality will usually be 'Not suspected.' The rationale for this guidance is that the symptoms of a lack of efficacy or progression of underlying illness are not caused by the trial drug, they happen in spite of its administration and/or both lack of efficacy and progression of underlying disease can only be evaluated meaningfully by an analysis of cohorts, not on a single participant
- 3. Its duration (start and end dates) or if the event is ongoing, an outcome of not recovered/not resolved must be reported
- 4. Whether it constitutes a SAE (see Section 10.1.2 for definition of SAE) and which seriousness criteria have been met
- 5. Action taken regarding study treatment.

All adverse events must be treated appropriately. Treatment may include one or more of the following:

- Dose not changed
- Dose Reduced/increased
- Drug interrupted/withdrawn
- 6. Its outcome (i.e., recovery status or whether it was fatal)

Conditions that were already present at the time of informed consent should be recorded in medical history of the participant.

Adverse events (including lab abnormalities that constitute AEs) should be described using a diagnosis whenever possible, rather than individual underlying signs and symptoms.

Adverse event monitoring should be continued for at least 30 days following the last dose of study treatment.

Once an adverse event is detected, it must be followed until its resolution or until it is judged to be permanent (e.g., continuing at the end of the study), and assessment must be made at each visit (or more frequently, if necessary) of any changes in severity, the suspected relationship to the interventions required to treat it, and the outcome.

Information about adverse drug reactions for the investigational drug can be found in the Investigator's Brochure (IB).

Abnormal laboratory values or test results constitute adverse events only if they fulfill at least one of the following criteria:

- they induce clinical signs or symptoms
- they are considered clinically significant
- they require therapy

Clinically significant abnormal laboratory values or test results must be identified through a review of values outside of reference ranges/clinically notable ranges, significant changes from baseline or the previous visit, or values which are considered to be non-typical in participants with the underlying disease. Alert ranges for laboratory abnormalities are included in Section 16.1 (Appendix 1).

10.1.2 Serious adverse events

An SAE is defined as any adverse event [appearance of (or worsening of any pre-existing)] undesirable sign(s), symptom(s), or medical conditions(s) which meets any one of the following criteria:

- fatal
- life-threatening

Life-threatening in the context of a SAE refers to a reaction in which the participant was at risk of death at the time of the reaction; it does not refer to a reaction that hypothetically might have caused death if it were more severe (please refer to the ICH-E2D Guidelines).

• results in persistent or significant disability/incapacity

- requires inpatient hospitalization or prolongation of existing hospitalization, unless hospitalization is for:
- routine treatment or monitoring of the studied indication, not associated with any deterioration in condition
- elective or pre-planned treatment for a pre-existing condition that is unrelated to the indication under study and has not worsened since signing the informed consent
- social reasons and respite care in the absence of any deterioration in the participant's general condition
- treatment on an emergency outpatient basis for an event not fulfilling any of the definitions of a SAE given above and not resulting in hospital admission
- is medically significant, e.g., defined as an event that jeopardizes the participant or may require medical or surgical intervention to prevent one of the outcomes listed above

Medical and scientific judgment should be exercised in deciding whether other situations should be considered serious reactions, such as important medical events that might not be immediately life threatening or result in death or hospitalization but might jeopardize the participant or might require intervention to prevent one of the other outcomes listed above. Such events should be considered as "medically significant." Examples of such events are intensive treatment in an emergency room or at home for allergic bronchospasm, blood dyscrasias, or convulsions that do not result in hospitalization or development of dependency or abuse (please refer to the ICH-E2D Guidelines).

All new malignant neoplasms will be assessed as serious under "medically significant" if other seriousness criteria are not met and the malignant neoplasm is not a disease progression of the study indication.

Any suspected transmission via a medicinal product of an infectious agent is also considered a serious adverse reaction.

All reports of intentional misuse and abuse of the product are also considered serious adverse event irrespective if a clinical event has occurred.

